## 1. STUDY RATIONALE

Intracranial atherosclerotic arterial stenosis (ICAS) is an important cause of stroke in the US, and is especially prevalent in blacks, Asians, and Hispanics. Over the past 20 years, [name], one of the Co-PIs of this pilot study has led consecutive NIH funded multicenter clinical trials to test therapies for preventing stroke in subjects with ICAS: The WASID trial showed that aspirin was as effective as warfarin for preventing stroke, and the SAMMPRIS trial showed that aggressive medical management (AMM) consisting of dual antiplatelet therapy and intensive risk factor management was more effective than percutaneous transluminal stenting for preventing stroke in recently symptomatic subjects with ICAS. However, among high-risk subjects (those with severe [70-99%] stenosis who presented with a stroke [rather than a TIA]), the 1-yr rate of recurrent stroke was 20.7% despite aggressive medical management. Therefore, more effective therapies to prevent stroke in these high-risk patients remains an urgent need.

One promising novel treatment is remote limb ischemic conditioning (RLIC), which involves producing repetitive, transient, non-injurious ischemia of a limb by inflating a blood pressure cuff proximally with the intention of protecting a distal organ (in this case, the brain) from subsequent ischemia. One of the co-investigators in our group ([name] at the Medical College of Georgia (MCG)) has conducted pre-clinical studies using a bilateral carotid artery stenosis mouse model that showed RLIC increases cerebral blood flow (CBF), most likely by releasing nitrite into the circulation, and acts as a powerful neuroprotectant and vasculoprotectant. Additionally, two pilot randomized clinical trials performed in China showed that symptomatic subjects with ICAS treated with bilateral upper extremity RLIC daily for 180 or 300 days and medical management had a 70-75% lower rate of stroke compared with subjects treated with medical management alone. Although these preclinical studies and the two small Chinese pilot studies might suggest that the next step is to perform a multicenter randomized Phase II trial to determine the potential efficacy of RLIC in high-risk subjects with ICAS in the US, the lack of reliable data on how RLIC works in humans mandates an initial earlier phase trial to study potential mechanisms of action of RLIC in subjects with ICAS.

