### 3. OVERVIEW OF STUDY DESIGN

The design of the study is illustrated in Figure 1 below. In this prospective randomized pilot study, 10 eligible high-risk subjects with ICAS will be randomized to RLIC (bilateral upper extremity (BUE) daily for 30 days) plus AMM (n=5) or AMM alone (n=5). The AMM, which will be started at study enrollment and continued until close-out in all subjects, will consist of aspirin 325 mg per day, clopidogrel 75 mg per day, and risk factor management primarily targeting a systolic BP < 140 mmHg and LDL cholesterol < 70 mg /dl. All subjects will undergo baseline brain arterial spin labeling (ASL) and perfusion MRI to measure CBF and have blood drawn for biomarkers 3-5 days after randomization to allow for washout of any effect from the test RLIC treatment that will be done prior to randomization to determine the subjects' tolerability to RLIC treatment (see section 5 for more details on screening test). The period of 3-5 days will provide flexibility for scheduling these tests. After the baseline MRI and biomarker tests are completed, the subjects randomized to RLIC will begin daily RLIC for 30 days. Each daily BUE RLIC treatment will consist of 4 cycles of 5-minute inflations of both blood pressure cuffs simultaneously to a pressure of 200 mm Hg with 5 minutes of reperfusion between each inflation using the Doctormate device (see Figure 2). All subjects will return for their close-out visits 33-35 days after enrolling in the study and will undergo brain ASL and perfusion MRI and have blood drawn for biomarkers at that visit. The study will be conducted at 4 sites (MUSC, MCG, UCLA, USC) to enable us to evaluate the consistency of CBF measurements across multiple sites and to ensure that the recruitment target of 10 subjects will be met in time to allow for the subsequent NIH grant submission in 2017.

Figure 1. Overview of Study Design

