Moreover, in terms of acute cardioprotection, pre-clinical studies have shown that 4 to 6 cycles of 5-minute durations appear optimal. Using 4 cycles instead of 5 cycles (the regimen used in the Chinese trials) will lessen the total duration of each treatment from 45 minutes to 35 minutes, which we expect will increase adherence. We chose to measure changes in CBF and biomarkers at 30 days for this pilot study because some preliminary human studies by the MCG group show that CBF increases within 6-24 hours of first use of RLIC, and a preclinical study (in a mouse model) shows that the increased CBF after RLIC is sustained to 28 days with daily RLIC treatment. Moreover, the first 30 days after enrollment in SAMMPRIS was the highest risk period for recurrent stroke so it is important to determine if the CBF and biomarker responses to RLIC persist for this period.

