d.) All of the medications used in this study (aspirin and clopidogrel and the medications to control risk factors) have been approved by the Food and Drug Administration (FDA) for the conditions for which they will be prescribed in this study and are not investigational. The major side effects of aspirin are major hemorrhage and peptic ulceration. Other possible side effects of aspirin include heartburn, ringing in the ears, nausea and vomiting. The most common side effects of clopidogrel are skin rash, bruising, itching, nausea, vomiting, diarrhea, intestinal discomfort. A less common but more serious side effect of clopidogrel is major gastrointestinal or brain hemorrhage. The most serious side effect of clopidogrel is a clotting disorder called thrombotic thrombocytopenic purpura (TTP) but this is very rare (1 in 15,000-20,000 treated subjects). The combination of clopidogrel and aspirin is commonly used for 90 days after stroke or TIA in patients with intracranial stenosis following the SAMMPRIS trial and will be prescribed for the duration that subjects participate in this pilot study (33-35 days). The combination of aspirin and clopidogrel is associated with a significantly higher risk of major bleeding compared with clopidogrel or aspirin alone. The risks associated with statin therapy are a persistent increase in liver enzymes (0.0 - 0.4%), myalgia (2.8%), muscle weakness with increase in CK levels > 10 x upper limit of normal (0.03 - 0.1%), and rarely rhabdomyolysis that can potentially lead to renal failure. The risks associated with antihypertensive medications include hypotension, dizziness, headaches, weakness,

allergic reactions, diarrhea, hypokalemia or hyperkalemia depending on the type of blood pressure medication taken, cough (with ACE inhibitors), and angioedema (ACE inhibitors).

e.) There is the risk of loss of confidentiality

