**Safety Monitoring.** [name] MD, Professor of Neurology at the Medical College of Georgia, will serve as the Safety Officer. [name] has over 30 years of experience as a vascular neurologist, is Board Certified in Internal Medicine and Neurology, and served as the Safety Officer for a past trial of minocycline in acute ischemic stroke conducted at the Medical College of Georgia, and two other sites. All adverse events (AE) and serious adverse events (SAEs) will be reported to [name] and the site's IRB within 24 hours. A SAE is defined by any medical experience regardless of its relationship to the investigational device or study drugs that occurs during subject enrollment in this trial that results in any of the following: (1) inpatient hospitalization or prolongation of a hospitalization; (b) persistent or significant disability/incapacity; (c) death of the study subject, or (d) necessitates an intervention to prevent a permanent impairment of a body function or permanent damage to a body structure. [name] will make a determination of whether an AE or SAE in any way is related to the Doctormate device.

Stopping rules: If the Safety Officer determines that an SAE is definitely related to the device, the study will be stopped and a review will be conducted by the safety monitor of the outcomes of all enrolled subjects, who will determine whether enrollment in the study can be restarted. Since there are only 10 subjects that will be enrolled in this pilot study, this decision to restart enrollment cannot be based on a formal statistical stopping rule. Instead it will be based on a clinical impression of likely harm to subjects from continuing ischemic conditioning, which the evidence from much larger completed trials of ischemic conditioning in subjects with coronary and intracranial occlusive disease suggests is very unlikely.

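### A review of all subjects' outcomes is required only after an SAE is called definitely device-related, although the Safety Officer judges relatedness of any degree

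*Combined protocol and SAP*

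**What the plan says.** The Safety Monitoring part of Section 13 has every AE and SAE reported to the Safety Officer and the site's IRB within 24 hours. The officer then "will make a determination of whether an AE or SAE in any way is related to the Doctormate device".

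The stopping-rule paragraph attaches one consequence to one outcome of that judgment: "If the Safety Officer determines that an SAE is definitely related to the device, the study will be stopped". Once that has happened, the safety monitor looks at how every subject in the trial has fared and decides whether enrollment can restart. The protocol says that 10 subjects are too few for a formal statistical rule, so that decision rests on a clinical impression of whether harm is likely.

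The protocol does not define what makes a relationship definite, gives no graded causality scale, and states no study-level step for an SAE that is related to a lesser degree.

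**The concern.** The officer is asked a broad question, but the plan acts only on its narrowest answer. The threshold for opening a review (definite causation) is also stricter than the standard used inside it (likely harm).

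This matters most for brain events. An injury under the cuff might be attributed with confidence. A single stroke or brain hemorrhage in an RLIC subject is different, because the protocol supplies another explanation for each. For stroke, Section 1 says that in this high-risk group "the 1-yr rate of recurrent stroke was 20.7% despite aggressive medical management", and Section 6 adds that "the first 30 days after enrollment in SAMMPRIS was the highest risk period for recurrent stroke". For hemorrhage, the risk analysis in Section 13 says of a drug that all subjects receive together with aspirin: "A less common but more serious side effect of clopidogrel is major gastrointestinal or brain hemorrhage". That such events would rarely be called definite is an inference, since the term is undefined, but a reasonable one.

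Followed to the letter, the plan would let a serious brain event judged probably device-related pass without a required look across subjects and without a recorded decision to continue.

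**Working it through.** **Text check.** The stopping rule states no figure to reproduce, so the check is to set each possible judgment beside what the plan requires.

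| Judgment on an SAE | Reporting | Study-level step stated |
|---|---|---|
| Unrelated | Safety Officer and IRB, 24 h | None |
| Related, short of definite | Safety Officer and IRB, 24 h | None |
| Definitely related | Safety Officer and IRB, 24 h | Stop, review of all subjects, restart decision |

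The other safety text does not fill the middle row:

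- Protection Against Risk (Section 13) provides an investigator call, an examination and a venous ultrasound. These concern the individual subject and are set off by questionnaire answers or symptoms, not by the causality judgment on an SAE.
- The four questions in Appendix 1 all concern the arms, as do the symptoms listed in the Appendix 2 diary.
- The risk analysis in Section 13 repeats the 24-hour IRB reporting of SAEs and deaths. That is notification, not review.

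**Review burden.** The fix below would also trigger on strokes caused by the underlying disease, so it is worth knowing how many to expect.

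Inputs:

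- One-year recurrent stroke risk of 20.7% (Section 1).
- Five RLIC subjects (Section 3).
- Baseline tests 3 to 5 days after randomization (Section 3), and then "After the baseline MRI and biomarker tests are completed, the subjects randomized to RLIC will begin daily RLIC for 30 days".
- "All subjects will return for their close-out visits 33-35 days after enrolling in the study" (Section 3).

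Assumptions: enrollment and randomization fall on the same day, the rate is constant, and RLIC has no effect on stroke.

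1. Yearly hazard: h = −ln(1 − 0.207) = 0.2319.
2. Time from first daily RLIC to close-out: shortest 33 − 5 = 28 days, longest 35 − 3 = 32 days.
3. Risk per subject, 1 − exp(−h × d/365): 1.76% at 28 days and 2.01% at 32 days.
4. Chance of at least one stroke among 5, 1 − exp(−5 × h × d/365): 8.5% at 28 days and 9.7% at 32 days.
5. Expected strokes among 5: 5 × 0.0176 = 0.088, and 5 × 0.0201 = 0.101.

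Section 6 suggests that risk is concentrated early, so a constant rate probably understates these figures, but the documents give no 30-day rate. For scale only, doubling the hazard gives 16.3% at 28 days and 18.4% at 32 days. Hemorrhages, deaths and other related SAEs would add reviews and cannot be counted from the documents.

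**Why a clinical review and not a test.** With 2 strokes in 5 RLIC subjects against 0 in 5 controls, the two-sided Fisher p-value is 2 × C(5,2)/C(10,2) = 20/45 = 0.44. Even a pattern that a clinician would want to look at is far from significant. This agrees with the protocol's own statement that no formal rule is possible.

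**The case against.** The strongest reply is that this is a drafting preference. One experienced vascular neurologist sees every event from a 10-subject trial within a day and judges the cause of each. The rule says when stopping is mandatory, and it does not say that the officer may act only then. Section 13 also gives reasons for expecting little harm. It reports no serious adverse event in either of the two earlier Chinese trials and no example, in animal or human experiments, of RLIC causing intracerebral hemorrhage. The device risks it anticipates are local arm problems, which are easier to attribute to a cuff and already have subject-level actions.

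Most of this stands, and it limits the point to a modest gain. It does not remove the point, because discretion leaves no required review and no record, and the events hardest to attribute are the ones least likely to meet the present trigger.

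A reader might infer more than the documents support:

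- *That SAEs short of definite go unreported or ignored.* They do not. All are reported and assessed, whatever their cause.
- *That the Safety Officer may not act on them.* Nothing in the text says so.
- *That 9% to 10% is the chance of missing a device harm.* That figure counts strokes assumed to be unrelated to RLIC. It measures how often the added review might be set off and says nothing about how often an SAE would be judged related but not definite.
- *That RLIC is suspected of causing brain hemorrhage.* Section 13 reports none.

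**Conclusion.** The point holds as a narrow one. The plan asks for a judgment on relatedness of any degree but requires a cross-subject review only when that judgment is definite, and no other section adds a study-level step. The mismatch can be read directly from the text. That brain events would seldom qualify is an inference from the competing causes that the protocol names.

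The effect is a modest one on patient safety. No aim, estimate, interval or sample size changes. How often the gap would matter cannot be estimated, because the documents give no basis for the frequency of SAEs judged related but not definite. It is a cheap improvement to consider, not an error that must be corrected.

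**What to change.** Keep the automatic stop for a definitely related SAE and add to the stopping-rule paragraph in Section 13:

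> Any SAE that the Safety Officer determines is in any way related to the device, and any stroke, intracranial hemorrhage or death in an RLIC subject after daily RLIC has started, leads to a prompt Safety Officer review of the outcomes of all enrolled subjects, with the decision to continue, pause or stop recorded. The trial continues meanwhile unless the Safety Officer decides otherwise.

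The first trigger uses the judgment that the officer already makes, so no new causality grades need defining. The second goes beyond judged relatedness on purpose, because attribution in a single subject is least reliable for these events.

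The cost is a couple of sentences and a few extra reviews at most, each covering no more than 10 subjects. Background stroke accounts for about 0.1 expected review at the constant rate, and other qualifying events would add to that. A background stroke would prompt a review but would not by itself halt the trial.

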
Subject Study Number \_\_\_\_\_

End of Week (Circle one) 1.\_\_\_\_\_, 2.\_\_\_\_\_, 3.\_\_\_\_\_, 4. (close-out visit) \_\_\_\_\_

Date\_\_\_\_\_

1.) Have you experienced any swelling in either of your arms? (Y/N)

*Coordinator Comment: (if yes, specify which arm(s) and where in the arm(s), i.e., above, at or below cuff)*

2.) Have you had any discoloration (change in color) in either of your arms after any treatment? (Y/N)

This could be redness, blueness, small red dots, red or purple blotches in your arm

*Coordinator Comment: (if yes, specify which arm(s), where in the arm(s), and type of discoloration)*

3.) Have you had any persistent tingling or numbness in either of your arms? (Y/N)

*Coordinator Comment: (if yes, specify which arm(s) and where in the arm(s))*

4.) During the cuff inflations or any time between use of the cuff, have you had pain in either arm? (Y/N)

*Coordinator Comment: if yes, ask subject to use visual analog pain scale given to subject after enrollment to rate the discomfort on the Pain scale between 0 and 10, and specify which arm(s) and where in the arm(s) is the pain located) Pain rating\_\_\_\_\_*

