### 4. SUBJECT SELECTION CRITERIA

**The Target Population** are subjects between 30 – 90 years of age with stroke within the previous 30 days that is attributed to 70-99% atherosclerotic stenosis of a major intracranial artery (carotid, middle cerebral, vertebral or basilar). The full inclusion and exclusion criteria are similar to the SAMMPRIS trial  (referred to in section 1 above) with the following exceptions: 1) Subjects with TIA will be excluded because of their excellent outcome on AMM in SAMMPRIS. 2) The upper age limit in this pilot is 90 rather than 80, given the positive response to RLIC in octogenarians in the 2nd Chinese trial. 3) CT angiography (CTA) or magnetic resonance angiography (MRA) measurements of 70-99% intracranial stenosis will be sufficient for enrollment in this study, whereas catheter angiography was required in SAMMPRIS. (Catheter angiography is expensive and has some risk that is difficult to justify in a medical management trial). 4) Diabetic subjects taking sulfonylureas will be excluded because these drugs block ATP-sensitive potassium channels that are thought to play a key role in the protective effect of RLIC. The full inclusion and exclusion criteria for this pilot study are provided below.

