### **Inclusion Criteria:**

1. Symptomatic cerebral infarction within 30 days of enrollment attributed to 70-99% stenosis of a major intracranial artery (carotid artery, MCA stem (M1), vertebral artery, or basilar artery) that is documented by any of the following: MRA, CTA, or catheter angiography. Percent stenosis will be measured according to WASID criteria ( $= 1 - [Ds / Dn] \times 100\%$  with Ds [diameter of stenosis] and Dn [diameter of normal vessel]).
2. Modified Rankin score of  $\leq 3$
3. Age  $\geq 30$  years and  $\leq 90$  years.
  - Subjects 30-49 years are required to meet at least one additional criteria (i-vi) provided in the table below to qualify for the study. This additional requirement is to increase the likelihood that the symptomatic intracranial stenosis in subjects 30-49 years is atherosclerotic.

i. insulin dependent diabetes for at least 15 years
ii. at least 2 of the following atherosclerotic risk factors: hypertension (BP $\geq 140/90$ or on antihypertensive therapy); dyslipidemia (LDL $\geq 130$ mg /dl or HDL $< 40$ mg/dl or fasting triglycerides $\geq 150$ mg/dl or on lipid lowering therapy); smoking; non-insulin dependent diabetes or insulin dependent diabetes of less than 15 years duration; family history of any of the following: myocardial infarction, coronary artery bypass, coronary angioplasty or stenting, stroke, carotid endarterectomy or stenting, peripheral vascular surgery in parent or sibling who was $< 55$ years of age for men or $< 65$ for women at the time of the event
ii. history of any of the following: myocardial infarction, coronary artery bypass, coronary angioplasty or stenting, carotid endarterectomy or stenting, or peripheral vascular surgery for atherosclerotic disease
iv. any stenosis of an extracranial carotid or vertebral artery, another intracranial artery, subclavian artery, coronary artery, iliac or femoral artery, other lower or upper extremity artery, mesenteric artery, or renal artery that was documented by non-invasive vascular imaging or catheter angiography and is considered atherosclerotic
v. aortic arch atheroma documented by non-invasive vascular imaging or catheter angiography
vi. any aortic aneurysm documented by non-invasive vascular imaging or catheter angiography that is considered atherosclerotic

4. Negative pregnancy test in a female who has had any menses in the last 18 months
5. Subject is willing and able to return in 30 days for close-out visit for the study

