6. Subject is available by phone
7. Subject is able to apply the conditioning device or has access to another person (family member, friend) who can assist with application of conditioning device if needed
8. Subject understands the purpose and requirements of the study, can make him/herself understood, and has provided informed consent
9. Subject is able to undergo brain MRI

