### **Exclusion Criteria:**

1. Previous treatment of target lesion with a stent, angioplasty, or other mechanical device, or plan to perform one of these procedures
2. Plan to perform concomitant angioplasty or stenting of an extracranial vessel tandem to an intracranial stenosis
3. Intracranial tumor (except meningioma) or any intracranial vascular malformation
4. Thrombolytic therapy within 72 hours prior to enrollment
5. Progressive neurological signs within 24 hours prior to enrollment
6. Any intracranial hemorrhage (parenchmal, subarachnoid, subdural, epidural) within 90 days
7. Any untreated chronic subdural hematoma

8. Intracranial arterial stenosis due to arterial dissection, Moya Moya disease; any known vasculitic disease; herpes zoster, varicella zoster or other viral vasculopathy; neurosyphilis; any other intracranial infection; any intracranial stenosis associated with CSF pleocytosis; radiation induced vasculopathy; fibromuscular dysplasia; sickle cell disease; neurofibromatosis; benign angiopathy of central nervous system; post-partum angiopathy; suspected vasospastic process, suspected recanalized embolus
9. Presence of any of the following unequivocal cardiac sources of embolism: chronic or paroxysmal atrial fibrillation, mitral stenosis, mechanical valve, endocarditis, intracardiac clot or vegetation, myocardial infarction within three months, dilated cardiomyopathy, left atrial spontaneous echo contrast, ejection fraction less than 30%
10. History of upper extremity ischemia, known subclavian or brachial artery stenosis, subclavian steal syndrome, any upper extremity soft tissue, orthopedic or vascular injury, or mastectomy or other procedure that may contraindicate taking blood pressure or having a cuff on the arm for the conditioning treatment
11. Difference in systolic blood pressure of > 15 mm Hg between both arms
12. Known allergy or contraindication to aspirin or clopidogrel
13. Active peptic ulcer disease, major systemic hemorrhage within 30 days, active bleeding diathesis, platelets < 100,000, hematocrit < 30, INR > 1.5, clotting factor abnormality that increases the risk of bleeding, current alcohol or substance abuse, uncontrolled severe hypertension (systolic pressure > 180 mm Hg or diastolic pressure > 115 mm Hg), severe liver impairment (AST or ALT > 3 x normal, cirrhosis), subject on dialysis

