14. Major surgery (including open femoral, aortic, or carotid surgery, cardiac) within previous 30 days or planned in the next 30 days after enrollment
15. Indication for warfarin or heparin beyond enrollment (**NOTE: exceptions allowed for subcutaneous heparin for deep vein thrombosis (DVT) prophylaxis while hospitalized**)
16. Diabetic subjects taking sulfonylurea drugs
17. Severe neurological deficit that renders the subject incapable of living independently
18. Dementia or psychiatric problem that prevents the subject from following the protocol reliably
19. Co-morbid conditions that may limit survival to less than 3 months
20. Pregnancy or of childbearing potential and unwilling to use contraception for the duration of this study
21. Claustrophobia requiring sedation for MRI or any metallic implants or MRI incompatible devices that do not permit the patient to have an MRI
22. Enrollment in another study that would conflict with the current study

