### **Protection Against Risk**

The research coordinator will call subjects randomized to the RLIC group weekly and will use a standardized questionnaire to ask subjects about adverse events (see Appendix 1). For the pain question, we will utilize a visual analog pain scale of 0 to 10 and provide this to the subjects randomized to the RLIC group. At the weekly phone call, the research coordinator will ask the degree of pain using this scale. If the score is > 2, the site investigator will be notified and will contact the subject by phone to review the level of discomfort. Additionally, If the subject answers "yes" to any other questions, we will ask the subject to come in to be examined. If we suspect a venous thrombosis because of swelling or pain, we will perform a venous ultrasound to rule out a deep venous thrombosis. We will also obtain the phone number of a relative or friend in order to reach the subject if we have trouble reaching the subject. All subjects will be given the telephone numbers of the principal site neurologist and site coordinator to report any clinical events or to ask questions about the study.

Subjects who are claustrophobic will not be enrolled in this study. To reduce the risk of phlebotomy, only trained phlebotomists will perform venipuncture. All neuroimaging and biomarker data will be de-identified as stated under "Sources of Material". Copies of the source documents used to collect data for study subjects will be kept in confidential binders at the participating sites. All these measures will ensure against loss of confidentiality.

Side effects of any medications prescribed to subjects as part of routine care of subjects with intracranial stenosis will also be monitored. These side effects will be minimized by recommending use of enteric-coated aspirin, checking liver enzymes and CK for subjects on a statin if clinically indicated, and instituting appropriate treatment should side effects arise.

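### The arm-symptom form in Appendix 1 has no pre-treatment administration, so pre-existing stroke-related swelling or numbness can be counted as on-treatment events in the RLIC group

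*Combined protocol and SAP*

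**What the plan says.** **The form.** The Appendix 1 time field, "End of Week (Circle one", offers weeks 1, 2, 3 and 4, the last being close-out. There is no baseline option. Item 3 reads "Have you had any persistent tingling or numbness in either of your arms? (Y/N", and item 1 asks about arm swelling in the same open way. A yes to any item prompts the coordinator to note which arm and where.

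**Who gets it and what follows.** Under Protection Against Risk (section 13), the coordinator calls RLIC subjects weekly with this questionnaire. A pain score above 2 leads to a call from the site investigator. After a yes to any other item, "we will ask the subject to come in to be examined". Under Safety Monitoring, all adverse events go to the Safety Officer and the site's IRB within 24 hours, and the Safety Officer decides whether each is related to the device.

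**Who is enrolled.** Section 4 targets subjects "with stroke within the previous 30 days". Inclusion 1 requires "Symptomatic cerebral infarction within 30 days of enrollment attributed to 70-99% stenosis of a major intracranial artery", and inclusion 2 allows a modified Rankin score of up to 3. Exclusion 17 removes only "Severe neurological deficit that renders the subject incapable of living independently". Exclusion 10 begins "History of upper extremity ischemia, known subclavian or brachial artery stenosis, subclavian steal syndrome, any upper extremity soft tissue, orthopedic or vascular injury". Inclusion 7 admits a subject who cannot apply the device alone but "has access to another person (family member, friend) who can assist with application of conditioning device if needed".

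**What is measured before treatment.** Section 3 lists MRI and blood biomarkers, 3-5 days after randomization and before daily RLIC starts.

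**The concern.** Tolerability is part of primary aim 3, and Appendix 1 is the structured symptom form behind it. The harms that it looks for overlap with what a recent stroke can leave behind. Section 13 lists arm swelling and muscle or nerve injury among the possible device risks, and also mentions numbness and tingling. If a symptom was there before the first session and the form cannot say so, two things suffer.

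- **The tolerability summary.** An old symptom can be counted as having occurred on treatment. With five RLIC subjects, one such case changes the picture.
- **The relatedness judgement.** The Safety Officer has to separate stroke deficit from cuff effect without a pre-treatment answer to the same question. A subject already at yes who gets worse at the same site stays at yes.

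The questionnaire is described for the RLIC group only, so there is no concurrent AMM-alone response to show how often such symptoms occur without the device.

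**Working it through.** No stated figure in the plan bears on this point, so the check is mainly a comparison of texts, followed by an illustration of size.

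**1. Timing.** The sequence in sections 3, 5 and 10 and the appendices is: a test inflation of 5 minutes before randomization, described as a tolerability check; baseline MRI and blood draw 3-5 days after randomization; daily RLIC; Appendix 1 at the end of weeks 1 to 4. The Appendix 2 diary starts at Day 1. No symptom record on either form precedes the first daily session.

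**2. Item wording.**

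| Item | Symptom | Tied to cuff or treatment? | Asks if new or worse? | Detail recorded |
|---|---|---|---|---|
| 1 | Swelling | No | No | Arm, location |
| 2 | Discoloration | Yes, after a treatment | No | Arm, location, type |
| 3 | Tingling, numbness | No | No | Arm, location |
| 4 | Pain | Yes, during or between cuff uses | No | Arm, location, 0-10 score |

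The weakness lies in items 1 and 3.

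**3. Eligibility.** Inclusions 1 and 2 with exclusion 17 admit a recent infarct with residual deficit short of loss of independent living. Exclusion 10 concerns ischemia, stenosis, injury or procedures of the arm, and exclusion 11 a blood pressure difference between arms. Neither removes stroke-related numbness or swelling.

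**4. Path of an old symptom.** A subject with persisting numbness from the qualifying stroke truthfully answers yes to item 3 on up to four forms. The calls for weeks 1 to 3 can each lead to a request to attend; at close-out the subject is already there. The form looks the same whether the numbness predates RLIC or began with it.

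**5. Size, for illustration only.** Input from section 3: n = 5 on RLIC. Let p be the proportion with arm swelling, tingling or numbness at entry. The documents do not give p, so it is assumed.

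- P(at least 1 of 5) = 1 − (1 − p)^5
- P(at least 2 of 5) = 1 − (1 − p)^5 − 5p(1 − p)^4
- Expected affected subjects = 5p; expected forms with a pre-existing yes, out of 5 × 4 = 20, = 20p if the symptom persists

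| Assumed p | At least 1 of 5 | At least 2 of 5 | Expected subjects | Expected forms of 20 |
|---|---|---|---|---|
| 10% | 1 − 0.590 = 41% | 8% | 0.5 | 2 |
| 20% | 1 − 0.328 = 67% | 26% | 1.0 | 4 |
| 30% | 1 − 0.168 = 83% | 47% | 1.5 | 6 |
| 50% | 1 − 0.031 = 97% | 81% | 2.5 | 10 |

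One such subject moves a simple count from 0/5 (exact 90% interval 0% to 45%) to 1/5 (1% to 66%). The intervals overlap widely. The harm is to the meaning of the count more than to any precise estimate.

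**The case against.** A reader might infer that the plan records stroke symptoms as device adverse events. It does not. Section 10 says that the calls document device problems or any adverse events, a yes leads to an examination, and the Safety Officer decides relatedness separately. Misattribution is a risk, not the planned rule.

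A reader might also infer that worsening can never show, or that all four items are unanchored. Neither holds. Spread to the other arm or to a new location would appear in the coordinator's notes, pain has a 0-10 score, and items 2 and 4 are tied to treatment or cuff use. Only same-site worsening in items 1 and 3 is invisible on the form.

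Other sources help. The diary has numbered daily rows with free text and can show a symptom already present on Day 1, or whether week-1 petechiae recurred or were merely reported again. Eligibility rests on routine evaluations that include a Rankin score and neurological status. It would therefore be too much to say that stroke deficit cannot be told from nerve injury. These sources still do not give a pre-treatment answer to the same items, and the diary has no row before Day 1.

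Two limits stand. Part of the text between section 5 and the later part of section 6 was not available, so a baseline examination described there cannot be ruled out. And qualifying strokes include vertebral and basilar territory, and inclusion 7 offers help only if needed, so arm symptoms in any given subject are possible rather than expected.

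Finally, broad symptom capture with later adjudication is a defensible choice in a 10-subject pilot. That argues for leaving the questions as they are; it does not argue against a baseline.

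**Conclusion.** The point holds as a modest, inexpensive improvement. In the available text the form has no pre-treatment administration, items 1 and 3 do not separate old symptoms from new ones, and subjects who may have such symptoms are eligible. Pre-existing symptoms can therefore enter the RLIC group's on-treatment events with neither a baseline nor a control response on this form to set them against.

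The size is unknown. The 41% to 97% range for at least one affected subject rests wholly on an assumed prevalence of 10% to 50% and on independence between subjects. Section 12 defines no adverse-event rate, so the shift from 0/5 to 1/5 describes the simplest summary that one would make for aim 3, not a planned statistic. The documents do not support the stronger conclusions that device attribution is automatic or that the safety process cannot work.

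**What to change.** 1. Complete Appendix 1 once at the existing baseline MRI and blood-draw visit, before the first daily RLIC session, recording arm and location. On that sheet, items 2 and 4 are read as present or absent at the visit.
2. Keep the current questions and the examination trigger unchanged. Rewording the items to ask only about new or worse symptoms would narrow what leads to an examination. Instead, add a field to each item: present before first treatment? new or worse since last contact?
3. Report tolerability in two ways: all symptoms, and symptoms new or worse than baseline.
4. Give the baseline sheet to the Safety Officer with each report.

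The cost is one four-item sheet per subject at a visit that already takes place, and one added field on the form. No extra visit or procedure is needed.
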